1.1 STUDY SCHEMA

1.2 SCHEDULE OF EVENTS (SOE)

Study Procedures & Assessments	Visit Schedule									
	Week									
	BL	Intake	1	2	4	13	26	39	52	
Consent	R									
Randomization (when determined eligible)		R								
Interventions (mCPT with or without CRP)										
Massed Cognitive Processing Therapy (mCPT)					1x/day					
Crisis Response Planning (CRP) or Treatment as Usual (TAU)					R					
Booster Sessions										up to 3 over the follow-up year
Adverse Event Reporting		R	R	R	R	R	R	R	R	R
Assessments:	R	R	R	R	R	R	R	R	R	R
1. Demographic and Military Service Characteristics	x									
2. History of Head Injuries Questionnaire + Addendum (HHI+HHI-A)	x									
3. Self-Injurious Thoughts and Behaviors Interview-Revised (SITBI-R)	x I	x* SR	x* SR	x* I						
4. Scale for Suicide Ideation (SSI)	x	x	x	x	x	x	x	x	x	x
5. Interpersonal Needs Questionnaire (INQ)	x					x	x	x	x	x
6. Beck Hopelessness Scale (BHS)	x					x	x	x	x	x
7. Suicide Cognitions Scale-Revised (SCS-R)	x	x	x	x	x	x	x	x	x	x
8. Difficulties with Emotion Regulation Scale-Short Form (DERS-SF)	x					x	x	x	x	x

Abbreviated Title: mCPT+CRP

Version Date: 07/10/25

9. Monetary Choice Questionnaire (MCQ)	x				x	x	x	x
10. Behavioral Inhibition System and the Behavioral Activation System (BIS/BAS)	x				x	x	x	x
11. Clinician Administered PTSD Scale for DSM-5 (CAPS-5) with Selection of Index Events (SOIE)	x							
12. Life Events Checklist (LEC)	x							
13. PTSD Checklist for DSM-5 (PCL-5)**		x	x	x	x	x	x	x
14. Posttraumatic Cognitions Inventory (PTCI-9)		x	x	x	x	x	x	x
15. Satisfaction with Therapy and Therapist Scale – Revised (STTS-R)			x					
16. Cornell Services Index-Short Form (CSI-SF)	x				x	x	x	x
17. PROMIS Computer Adaptive Tests (PROMIS- CATs)		x	x	x	x	x	x	x
18. Clinical Global Impression (CGI)			x	x				
19. Ecological Momentary Assessment (EMA)			6x/day for 28 days					
20. Fitbit			for 28 days					
21. Qualitative Interview				x				
All activities are for research. * “Since your last assessment” version ** “In the past week” version for all assessments. I = Interview; SR =Self-report								

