6.6.2 CompensationN/A

- Participants can be compensated for completing follow-up assessments using the following schedule:
 - \$50 for the posttreatment qualitative interview
 - \$25 at 1 month
 - \$25 at 3 months
 - \$25 at 6 months
 - \$25 at 9 months

Abbreviated Title: mCPT+CRP

Version Date: 07/10/25

- \$50 at 12 months

Participants will also be compensated for completing EMA surveys and wearing their Fitbits.

Participants will be compensated based on the number of EMA surveys completed per week:

- \$20 per week for completing at least 75% of EMA surveys (32 of 42 surveys) and wearing their Fitbit at least 75% of days (5 of 7 days) per week (total \$80 for the four weeks) or
- \$30 per week for completing at least 90% of EMA surveys (38 of 42 surveys) and wearing their Fitbit at least 90% of days (6 of 7 days) per week (total of \$120 for the four weeks).

This yields a maximum possible compensation of \$120 for EMA completion and Fitbit wear, totaling \$320 of possible compensation for all study activities. Participants will be allowed to keep the Fitbit.

- As required by UTHSCSA, these funds will be distributed using the university ClinCard system.
- Payment will be provided via a rechargeable MasterCard® ClinCard. The MasterCard® ClinCard is a debit card issued to the study participant. Funds are loaded onto the card through the ClinCard website at www.clincard.com. Only authorized users are able to access the ClinCard website with a username and password to add funds. The ClinCard funds will typically be available to recipients within one business day but payment could take up to 2 weeks. ClinCard funds can be used as the participant chooses. The participant will be notified that their name, social security number, address and date of birth will be shared with a third-party (ClinCard) for the purposes of payment processing. This information will be used for the administration of the payment and will be kept strictly confidential.

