8.2 PARTICIPANT DISCONTINUATION/WITHDRAWAL FROM THE STUDY

Participants are free to withdraw from participation in the study at any time upon request.

An investigator may discontinue a participant from the study for the following reasons:

- Participant does not meet inclusion/exclusion criteria.

Abbreviated Title: mCPT+CRP

Version Date: 07/10/25

- An event or medical condition or situation occurs such that continued participation would not be in the best interest of the participant or might require an additional treatment that would confound the interpretation of the study.
- The participant does not follow the study procedures resulting in significant non-compliance.
- Lost-to-follow up; unable to contact participant.
- Participant has completed the study follow-up period.

The reason(s) for participant discontinuation or withdrawal from the study will be recorded in the study database. Participants who sign the informed consent form and are randomized but who never begin the study intervention may be replaced. Participants who sign the informed consent form, are randomized and receive the study intervention but who subsequently withdraw or are discontinued from the study will not be replaced.

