9.2 STUDY EVALUATIONS & PROCEDURES

9.2.1 Visits and Procedures

Visits: See Table in Section 1.2 (Visit Schedule Study Procedures and Assessments) for Study Visits.

Procedures:

- Individuals referred by their provider for consideration of the study or who self-refer in response to study advertisements will have a brief discussion with a member of the study team where the basic study inclusion and exclusion criteria will be reviewed to help the individual determine if he or she meets the study criteria or has obvious exclusions from the study protocol so as to prevent individuals from taking unnecessary time for consent and more in-depth screening.
- Following consent, participants will complete the baseline assessment. The baseline assessment will include questionnaires and interviews and will last 2-3 hours in total.
- Once confirmed eligible, the participant will be randomly assigned into one of the two study arms, Crisis Response Planning (CRP) or Treatment as Usual (TAU). Regardless of which study arm the participant is randomized to, all participants will receive Massed Cognitive Processing Therapy (mCPT). This information will be conveyed to the participant during a 1½ -hour Intake Appointment. During this appointment additional questionnaires will be completed either on paper or on the computer. Also at this time, the participant will sync their Fitbit or a Fitbit provided by the study staff with Fitabase and load the EMA app onto the participant's phone. The data collection through Fitabase and EMA prompts will start at this time and continue for 28 days.
- CPT sessions will be scheduled daily for 10 consecutive business days (i.e., “massed” CPT), with the first appointment being 1-2 weeks post-intake. Participants will be allowed to schedule up to 3 optional “booster sessions” during the follow-up year to review skills learned in therapy and receive additional support and/or coaching after the acute treatment. Each of the 10 treatment sessions and up to 3 optional booster sessions will last 1-hour.
- Within 1 month of ending therapy, participants will complete one 45–60-minute semi-structured interview with study staff.
- Follow-up assessments will be completed 4-, 13-, 26-, 39-, and 52-weeks following treatment. Each follow-up will last 30-45 minutes.

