10.4.2 Analysis of the Primary Endpoints

Hypothesis 1: The rate of follow-up suicidal behavior will be significantly reduced among military personnel receiving CRP versus usual care risk management in addition to massed CPT.

Survival analysis with time-to-suicide attempt will be used to test overall differences between the two intervention groups. We will use the hazard ratio derived from the Cox regression supplemented with the log-rank and Wilcoxon statistics derived from the Kaplan-Meier method. Time will be calculated as number of days since the intake appointment. Multiple suicide attempts within participants will be handled using the Andersen-Gill counting process model (Anderson & Gill, 1982), which assumes that the time increments between multiple suicide attempts can be explained by past suicide attempts (e.g., shorter time intervals between suicide attempts are more likely among patients who have previously attempted suicide). **Power Analysis:** Power calculations for H1 were conducted using PROC POWER in the SAS 9.4 software. Anticipated suicide attempt rates were based on previously published clinical trials conducted within and external to the military. In previous studies of cognitive behavioral therapies for suicide prevention, the suicide attempt rate in the usual care conditions often ranges from 40-50% during the first year and active suicide-focused interventions typically have 50% lower suicide attempt rates (Brown et al., 2005; Gysin-Maillart et al., 2016; Linehan et al., 1991; Rudd et al., 2015). In our previous RCT of CRP versus usual care ([name] et al., 2017), participants receiving CRP were 76% less likely to attempt suicide. Results of our pilot study of massed CPT yielded a similar 73% reduction in suicide attempts in the CRP group versus usual care. We therefore estimated statistical power for hazard ratios ranging from 0.50-0.75 when suicide attempt rates in usual care ranged from 30-50%, assuming 15% attrition, 1-year follow-up, and a two-tailed $p<.05$. $N=150$ yielded $>80\%$ power under nearly all conditions.

Hypothesis 2: Reductions in the severity of suicidal ideation will be significantly larger among military personnel receiving CRP versus usual care risk management.

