We will sum the number of EMA responses during which participants endorsed the use of their CRP (and safety plan), such that higher values indicate more frequent intervention use. This count variable will be entered into a Cox regression model predicting time to suicide attempt and a linear regression model predicting change in SSI score to assess the correlation of intervention use with, respectively, follow-up suicidal behavior and severity of suicidal ideation. We will construct separate models for each treatment group. To test the specificity of our findings to CRP, we will repeat these analyses with CPT homework completion, also assessed during EMA and calculated as the sum of positively endorsed EMA responses, entered as a covariate. **Power Analysis:** The power analysis for H4 mirrors the power analysis for H3 above.

Exploratory Research Question 2: Which treatment components and design features do participants find most helpful for reducing suicidal ideation and attempts?

We will use descriptive statistics of participant characteristics, chi-squared tests, and Pearson correlations (where applicable) to explore relationships among personal experiential themes, group experiential themes, and participant characteristics. **Power Analysis:** Recommendations for minimum sample size in qualitative studies using IPA typically range from 2-25 participants, depending on the homogeneity that exists within participants' lived experience (Alase, 2017; Smith et al., 1999). Because we plan to interview all enrolled participants, our sample size will be more than adequate.

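### Hypothesis 4 enters plan use summed over the 28 days after intake as if known at day 0 in a Cox model that counts time from intake

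*Protocol*

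**What the plan says.** Protocol section 10.4.2, Hypothesis 4, builds the exposure as a single total per participant: "We will sum the number of EMA responses during which participants endorsed the use of their CRP" or safety plan. It continues: "This count variable will be entered into a Cox regression model predicting time to suicide attempt". A linear model for change in SSI uses the same total. Models are fitted separately by arm and then repeated with CPT homework completion, "also assessed during EMA and calculated as the sum of positively endorsed EMA responses, entered as a covariate".

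Hypothesis 4 gives no time origin of its own. The one stated for time to attempt is under Hypothesis 1 in the same section: "Time will be calculated as number of days since the intake appointment". On EMA timing, section 9.2.1 says of the intake appointment: "The data collection through Fitabase and EMA prompts will start at this time and continue for 28 days". The Schedule of Events (section 1.2) agrees: "6x/day for 28 days".

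No section gives Hypothesis 4 a landmark, delayed entry, a time-updated count or a divisor for surveys answered.

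**The concern.** A fixed covariate in a Cox model has to be known when the clock starts. Here it is complete only 28 days later, so a participant who attempts on day 10 enters the risk sets with a total that should run to day 28.

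What follows depends on EMA after an attempt, which the protocol does not settle. Section 8.2 lets an investigator withdraw a participant when "An event or medical condition or situation occurs such that continued participation would not be in the best interest of the participant"; admission, death or non-response are other routes. If EMA stops or thins out, early attempters get low totals because they attempted. Dropout without an attempt is censoring and does not create this bias.

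Separately, the sum mixes how often the plan is used with how many surveys are answered.

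Hypothesis 4 is correlational, and the randomised evidence lies in Hypotheses 1 and 2. But it is the planned test of whether more plan use goes with fewer attempts. As specified, its estimate would not separate a real association from this artefact in either arm.

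**Working it through.** The protocol gives no figure to reproduce. The check concerns timing first, then size.

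**Timing.** Risk sets open at day 0 (intake). The exposure closes at day 28, with up to 6 × 28 = 168 prompts. As an illustration, assume 75% of prompts answered and use endorsed in 10% of responses. The full-window expectation is 168 × 0.75 × 0.10 = 12.6. If EMA stops at an attempt on day 10, it is 60 × 0.75 × 0.10 = 4.5, with no difference in the person's rate of use.

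**Sum versus rate.** Section 6.6.2 sets pay thresholds at 32 and 38 of 42 weekly surveys, which is 128 and 152 over four weeks. At the same 10% use rate:

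- 84 answered (half of 168): 8.4
- 128 answered: 12.8
- 152 answered: 15.2

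**Size under no true effect.** Simulation of one arm, n = 75, 2,000 runs per setting, Cox Wald test at 0.05.

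- From the protocol: 150 participants, 6 prompts a day for 28 days, 15% attrition, attempt rates of 20% (Hypothesis 3 power) and 30% (low end for Hypothesis 1).
- Assumed: dropout uniform over the year; mean response 75% (SD about 15%); mean use 10% of responses, between-person CV 0.5–1.0 (also 0.3 for the full stop); homework 15%, independent of use; the share of attempts in the first 28 days; EMA behaviour after an attempt. Attempts spread evenly put 8–9% of them in the first 28 days.

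| EMA after an attempt | Share of attempts by day 28 | HR per SD of use | Type I error |
|---|---|---|---|
| Continues unchanged | range over settings | 0.98–1.01 | 4.3–5.6% |
| 3-day gap | range over settings | 0.93–0.98 | 3.5–5.6% |
| Half of attempters stop | 8–9% | 0.96–0.97 | 4.2–5.0% |
| Half of attempters stop | 25% | 0.89–0.94 | 3.4–6.7% |
| All attempters stop | 8–9% | 0.89–0.95 | 3.9–8.7% |
| All attempters stop | 25% | 0.74–0.86 | 3.8–24.5% |
| All stop, homework covariate added | 25% | 0.75–0.87 | 3.8–22.4% |

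The homework covariate does not help because it is a sum truncated in the same way. At a mid-range use CV (0.7–0.75), full stop with 25% early gives type I error of about 7.5–10.6%; the top of the range needs the least favourable inputs. A stress case with 40% early and a full stop gives HR 0.58–0.79 and error 6.0–50.7%.

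A differently built simulation (gamma-Poisson use, attempt rates 20% and 40%, full stop) gave median HRs of 0.94–0.95, 0.89 and 0.77 for 7%, 15% and 30% of attempts in the window. The false protective rate, nominally 2.5%, ran from 2.7% to 10.0% at the 20% attempt rate and from 3.4% to 20.8% at 40%.

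**Repairs under the same null.**

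- Landmark at the end of EMA with a use rate: HR 0.96–1.01, type I error 3.5–5.6% in every setting in the table; error 3.8–5.3% in the stress case.
- Time-dependent use rate: HR 0.97–1.01, error 3.6–5.8%.
- Use rate with the intake clock and no landmark, full stop: HR 0.98–1.01, error 4.3–10.8%. The divisor removes most of the shift; the landmark restores the error rate.
- 35-day EMA with a day-35 landmark, full stop: error 4.1–5.6%.

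**The case against.** - **The clock is inferred.** Hypothesis 4 states neither its time origin nor its summing window, and an SAP could set them. That is true. But the protocol itself fixes the covariate as one total, the model as Cox and the outcome as time to attempt, and intake is the only origin it gives. Any origin before EMA ends leaves the same misordering, whether the window is 2 weeks, 28 days or 5 weeks.
- **EMA may well continue after an attempt.** Section 9.3 has EMA ask about suicidal behaviour, answer with an automated message, and forgo real-time monitoring. Nothing there stops EMA. If it runs on unchanged, this bias is absent. The text does not, however, secure EMA through admission or death.
- **The direction is not fixed.** If plan use rises 1.5 to 2 times after an attempt, the same look-ahead pushes the HR above 1: about 1.02–1.04 with an even spread and 1.07–1.15 with 25% early. Higher-risk participants using the plan more would also push it upward. This stands. It makes the estimate harder to read, and the same repair removes the look-ahead part.
- **The shift is small unless assumptions combine.** With an even spread and a full stop, an HR of 0.94 is about −0.06 on the log scale, roughly a quarter of the standard error (0.22–0.28). This stands too.
- **A sensitivity analysis could expose it.** Attempts and EMA are both dated, so this is feasible, but none is planned. It is simpler to specify the main model correctly.
- **A count is a legitimate dose measure.** It can be, but the protocol reads higher values as more frequent use, and a count confounds that with response rate.

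**Conclusion.** The point holds. As written, the Hypothesis 4 Cox model uses exposure recorded after some of the events it is meant to predict. Whether that biases the result depends on two things the protocol does not give: how many attempts fall in the EMA window, and whether an attempt interrupts EMA. The effect is nil if EMA continues unchanged and small if attempts are spread evenly (HR 0.89–0.95 even with a full stop). It is material if a quarter of attempts are early and all attempters stop (HR 0.74–0.86, type I error up to 24.5%). The dependence of the raw sum on surveys answered needs none of these assumptions. Confidence in the size is medium. Because Hypothesis 4 is correlational and Hypotheses 1 and 2 are untouched, this should be corrected but does not threaten the trial's main conclusions.

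**What to change.** State the time origin for Hypothesis 4, then choose one of:

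1. **Landmark.** Include participants who are attempt-free and in follow-up at the end of the EMA window, restart the clock there, and define exposure as endorsed responses divided by completed responses.
2. **Time-dependent covariate.** Keep every attempt and use the cumulative use rate to date.

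Compute the CPT homework covariate in the same way.

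Before fixing the landmark day, reconcile the EMA length. Sections 1.2 and 9.2.1 give 28 days, while Hypothesis 3 in section 10.4.2 counts on 5 weeks, including 2 weeks after treatment. CPT starts on day 7–14 and 10 business days span 12–14 calendar days, so session 10 falls between day 7 + 12 = 19 and day 14 + 14 = 28. A 28-day window then leaves 0–9 days after treatment.

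The cost is analysis wording. The landmark drops attempts made during EMA from Hypothesis 4 only; they stay in Hypothesis 1. Per 75-person arm, with constant hazard and no dropout, the loss is 75 × (1 − exp(−λL)), λ = −ln(1 − p)/365:

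- L = 28: 1.3 of 15 attempts (p = 20%) or 2.0 of 22.5 (p = 30%)
- L = 35: 1.6 or 2.5
- If 25% of attempts fall in the first 28 days: 0.25 × 15 ≈ 3.8 or 0.25 × 22.5 ≈ 5.6

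The time-dependent version loses none.

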10.4.3 Analysis of the Secondary Endpoint(s)

See Section 10.4.2 (Analysis of the Primary Endpoints) for the analysis plan for each of the study aims.

Abbreviated Title: mCPT+CRP

Version Date: 07/10/25

10.4.4 Safety Analyses

Not applicable.

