2.2 RISK/BENEFIT ASSESSMENT

2.2.1 Known Potential Risks

- Emotional distress including experiencing an initial increase of PTSD symptoms and suicidal ideation due to the discussion of traumatic events.
- Assessment and treatments may be associated with a temporary or occasional increase in symptoms of depression, anxiety, or other pre-existing psychiatric symptoms.
- Participants may experience skin irritation from wearing the Fitbit.
- Risk of breach of confidentiality while handling research data.

Abbreviated Title: mCPT+CRP

Version Date: 07/10/25

- One of the risks of PTSD, both in and out of treatment, is attempted suicide, which can result in death.

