2.2.2 Known Potential Benefits

The main benefit to participating in this research is the receipt of high-quality, closely supervised, trauma-focused therapy (i.e., massed CPT) and suicide risk monitoring at no cost to the participant. In addition, the knowledge gained from this study will serve to inform the most effective interventions for the treatment of elevated suicide risk among active duty service members and veterans diagnosed with PTSD.

2.2.3 Assessment of Potential Risks and Benefits, none of which are expected to negatively affect an active duty participant's fitness for duty.

Research procedures	Risks
Assessments (questionnaires, interviews, computer testing, EMA, wearing the Fitbit)	
 • Serious and likely; none • Serious and less likely; none • Serious and rare; breach of confidentiality with the use of online conferencing systems, handling medical and research records, EMA, and by the Fitabase service • Not serious and likely; discomfort, emotional distress, and a temporary increase in PTSD symptoms and suicidal ideation thinking about and completing assessments • Not serious and less likely; skin irritation from wearing the Fitbit
Massed CPT Crisis Response Planning	
 • May be Serious and likely; treatment can cause some discomfort or emotional distress and can even produce a temporary increase in symptoms • Serious and less likely; none • Serious and rare; breach of confidentiality with the use of online conferencing systems, handling medical and research records, and by the Fitabase service • Not serious and likely; none • Not serious and less likely; none

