6. STUDY POPULATION

Active duty service members and veterans at least 18 years of age seeking care for PTSD symptoms who have experienced active suicidal ideation within the past week and/or suicidal behavior within the preceding month.

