If, during the course of an EMA survey, a participant “flags” as being at current high risk for suicide, they are directed within the survey to a “we are concerned about you” message. This message will contain information expressing concern about the participant’s wellbeing, remind the participant that EMA responses are not actively monitored by the research team, and provide resources for the participant to reach out to for help (including the suicide prevention hotline and information about nearby emergency resources). The following criteria will be used to flag the “we care are concerned about you” message: Suicidal intent: defined as a score of 3 or higher (range 0-4) on the suicidal intent item, “how sure are you that you want to kill yourself?”; Suicidal Behavior: defined as a positive endorsement of the item, “have you done anything to hurt yourself with at least some intent or desire to die?” or selected any suicide-related behavior from the item, “In the past 2 hours, have you done any of the following.” See Appendices for the EMA MetricWire “we are concerned about you” Message.

All interview measures as well as indicated safety assessments will be performed by qualified personnel.

For this study, all Adverse Events Documents collected on patients for this protocol will be reviewed by the PIs at least monthly to determine if a serious safety problem has emerged that result in a change or early termination of the protocol such as:

- suspending enrollment due to safety or efficacy, or
- termination of the study due to a significant change in risks or benefits.

Any protocol modifications, problematic safety reports, unanticipated problems, and/or suspension or early termination of a study will be reported to all members of the research team, the UTHSCSA IRB, the CRDAMC Human Protections Director, the STRONG STAR Data Safety Monitoring Board (DSMB), the sponsor, and the funder according to each’s policies and guidance. Suspension and early termination of a study will be reported immediately to the STRONG STAR Data Safety Monitoring Board (DSMB), the sponsor, and the funder.

9.4 ADVERSE EVENTS AND SERIOUS ADVERSE EVENTS.

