Adverse Event definition: An adverse event (AE) is defined as any untoward or unfavorable medical occurrence in a human subject, including any abnormal sign (e.g., abnormal physical exam or laboratory finding), symptom, or disease, that is a change from baseline, whether or not considered related to the subject’s participation in the research. For this study, all adverse events will be documented at each study visit and be completed with the last study visit. Serious Adverse Event definition: A serious adverse event (SAE) is any adverse event that:

1. results in death;
2. is life-threatening (places the subject at immediate risk of death from the event as it occurred);
3. results in inpatient hospitalization or prolongation of existing hospitalization;
4. results in a persistent or significant disability/incapacity;
5. results in a congenital anomaly/birth defect; or
6. based upon appropriate medical judgment, may jeopardize the subject’s health and may require medical or surgical intervention to prevent one of the other outcomes listed in this definition.

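### Section 10.4.4 dismisses safety analysis although adverse events are recorded at every visit; beyond suicide attempts and ideation, no by-arm summary of harms is planned

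*Protocol*

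**What the plan says.** Section 10.4.4 (Safety Analyses) consists of the words "Not applicable" and nothing else.

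Other sections treat safety data as a working part of the trial:

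- **Collection.** Section 9.4 states: "For this study, all adverse events will be documented at each study visit and be completed with the last study visit". It then gives a six-part SAE definition that includes death and inpatient hospitalisation. The schedule of events in Section 1.2 has a row for AE reporting.
- **Population.** Section 6 enrols adults seeking care for PTSD symptoms "who have experienced active suicidal ideation within the past week and/or suicidal behavior within the preceding month".
- **Named risks.** Section 2.2.1 says: "One of the risks of PTSD, both in and out of treatment, is attempted suicide, which can result in death". The table in Section 2.2.3, in the row for massed CPT and CRP, says that "treatment can cause some discomfort or emotional distress and can even produce a temporary increase in symptoms".
- **Use in oversight.** Section 9.3 says that "all Adverse Events Documents collected on patients for this protocol will be reviewed by the PIs at least monthly". The possible outcomes it lists are "suspending enrollment due to safety or efficacy, or" ending the study because risks or benefits have changed materially. Section 11.2 allows closure after oversight bodies review AEs, and Section 11.5 places the trial under a separate data safety and monitoring plan.

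On between-arm comparisons, Section 10.4.2 compares time to suicide attempt (H1) and scores on the Scale for Suicide Ideation (H2). Section 10.4.1 makes all tests two-sided at 0.05. Section 10.3 promises comparisons of outcome measures and does not mention AEs.

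**The concern.** Section 10.4.4 answers the question of safety analysis; it does not leave it open. The neighbouring Sections 10.4.3 and 10.4.6 refer the reader to Section 10.4.2, and Section 10.4.7 at least says what it is declining to do. Section 10.4.4 does neither. A statistical analysis plan written to match it would have no safety analysis to specify, and one that added such an analysis would depart from the protocol.

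The entry conflicts with collecting AEs throughout follow-up and with letting them decide whether the trial continues. Followed as written, the trial could report a benefit of CRP with no planned account by arm of deaths, hospitalisations or other SAEs. Both arms receive massed CPT, so a harm linked to CRP as against safety planning could be seen only by setting the arms side by side.

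**Working it through.** The protocol gives no figure for safety, so there is nothing to reproduce. The check is a reading of the sections against each other, followed by two illustrations.

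**1. Which harms have a planned comparison by arm?**

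| Harm | Compared by arm? | Where |
|---|---|---|
| Suicide attempt, including repeat attempts | Yes, two-sided | Section 10.4.2, H1 |
| Suicidal ideation | Yes, two-sided | Section 10.4.2, H2 |
| Other scheduled scales (e.g. PCL-5, PROMIS) | Only under the general statement on outcome measures | Section 10.3 |
| Any AE, any SAE | None stated | Section 10.4.4 |
| Death, inpatient hospitalisation | None stated | Section 10.4.4 |

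H1 is written as time to suicide attempt and H2 as a scale score. Neither produces a count of deaths, hospitalisations or other SAEs. Section 9.3 describes review by the investigators and reporting to the monitoring board, and does not say whether events are summarised by arm.

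**2. What would a by-arm table show when no events are seen?**

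Inputs: 150 randomised (Section 1, synopsis), taken as 75 per arm on the assumption of equal allocation. With zero events in n participants:

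- exact two-sided 95% upper bound = 1 − 0.025^(1/n); for n = 75 this is 4.8%
- one-sided 95% upper bound = 1 − 0.05^(1/n); for n = 75 this is 3.9%

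If the 15% attrition assumed for H1 in Section 10.4.2 also applied here, n = 0.85 × 75 = 63.75, about 64 per arm. The bounds become 5.6% and 4.6%.

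**3. Should the table carry a formal test?**

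The protocol gives no harm rates, so those below are assumptions. With 75 per arm and two-sided 0.05, let SE0 = √(2p̄(1 − p̄)/75), where p̄ is the mean of the two rates, and SE1 = √([p1(1 − p1) + p2(1 − p2)]/75). Then power = Φ((|p2 − p1| − 1.96·SE0)/SE1), and the 95% half-width is 1.96·SE1.

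| Assumed rates | SE0 | SE1 | Power | 95% half-width (percentage points) |
|---|---|---|---|---|
| 5% vs 10% | 0.0430 | 0.0428 | 21% | 8.4 |
| 10% vs 20% | 0.0583 | 0.0577 | 40% | 11.3 |
| 10% vs 30% | 0.0653 | 0.0632 | 87% | 12.4 |

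At 63.75 per arm the three powers fall to 19%, 35% and 81%. Of these cases, only the threefold difference is detected reliably, so a descriptive table with confidence intervals is the sensible form.

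**The case against.** Several stronger readings are tempting, and the documents do not support them.

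- **That no harm is compared between arms.** H1 and H2 compare suicide attempts and ideation, and because the tests are two-sided an excess under CRP could be declared as readily as a benefit.
- **That worsening of symptoms goes unexamined.** Ideation is compared at each follow-up time. Section 10.3 promises comparisons of outcome measures, and the schedule includes PTSD and general mental health scales. That promise is thin, but it is not nothing.
- **That the monitoring board sees no data by arm.** The monitoring plan is a separate document and is not shown. Whether its reports are by arm is unknown.
- **That AEs will not be reported.** Section 10.4.4 does not forbid reporting; what is missing is a plan for it.

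Four further points are fair. By-arm AE tables are commonly left to the statistical analysis plan. The risk in Section 2.2.1 is attributed to PTSD and not to CRP, and no CRP-specific harm is named. The zero-event bound follows from the sample size and does not measure the defect. Finally, Section 9.4 does not show that psychiatric cause or relatedness is coded for each AE, so tables on those may need new data fields.

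These points limit the concern to AEs and SAEs outside H1 and H2, and make some table rows conditional. They do not remove it. Section 10.4.4 gives a stated answer, so the usual deference to a later plan does not apply, and that answer is inconsistent with Sections 1.2, 9.3, 9.4 and 11.2.

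**Conclusion.** The point holds in this limited form: a safety analysis is declared irrelevant in a trial that records AEs and SAEs throughout and can be halted on them, and apart from H1 and H2 no by-arm summary of AEs is planned. The conclusion rests on the text of the protocol and on no assumed rate. The 4.8% bound is an illustration that assumes 75 per arm with complete follow-up. The defect leaves the sample size and the primary inference unchanged. It weakens the benefit-risk statement that the trial could make, which matters in a population selected for recent suicidal ideation or behaviour. It should be corrected before the analysis is fixed.

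**What to change.** Replace the entry in Section 10.4.4 with a short paragraph along these lines: the number and proportion of participants with any AE, any SAE, death and inpatient hospitalisation will be summarised by randomised arm, with event counts and exact 95% confidence intervals and without formal testing; suicide attempts and suicidal ideation are analysed under H1 and H2 in Section 10.4.2.

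Death and inpatient hospitalisation are already SAE criteria in Section 9.4. Add rows for psychiatric hospitalisation and for AEs related to study procedures only if the case report forms capture cause and relatedness for each event. If a by-arm summary is already planned elsewhere, such as in the monitoring plan or the statistical analysis plan, Section 10.4.4 should point to it.

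The cost is one paragraph and a few descriptive tables. The core rows use information the protocol already calls for, and neither the sample size nor any study procedure changes.
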